1.2. Schedule of Activities (SoA)

1.2.1. Schedule of Activities for Part 1 (SAD)

Study Day	-28 to -1	-1		1								2	3	5	8 to 12 days after dosing	Early Discontinuation Visit (EDV)				
							Times	Afte	r Do	sing	(hou	rs)					Phone Call	Return Visit ^a	Follow-up Phone Call	
Study Procedures ^b	Screen	Adm	Pre- dose	0	0.25	0.5	0.75	1.5	2	3	4	6	8	12	16	24				
Informed Consent	Х																			
Medical History (including demographics)	х																			
Weight and Height c	Х		Х																	
Vein Assessment	Х																			
Urine Drug Screen (including Cotinine)	Х	Х																		
Alcohol Breath Test	Х	Х																		
Serum Pregnancy Test d	Х																			
Urine Pregnancy Test d			Х															Х		Х
Inhaler Device Training	Х		Х																	
IMP Administration				Х																
Discharge from the Clinic																X e				
Physical Examination f	Х	Х	Х	•	•		•	•		•	•	•			•	→		Х		Х
Safety Labs ^g	Х															Х		Х		Х
Serology (HIV/Hepatitis screen)	Х																			

Study Day	-28 to -1	-1		1													3	5	8 to 12 days after dosing	
							Times	Afte	r Do	sing	(hou	ırs)				Phone Call	Return Visit ^a	Follow-up Phone Call		
Study Procedures ^b	Screen	Adm	Pre- dose	0	0.25	0.5	0.75	1.5	2	3	4	6	8	12	16	24				
FSH (postmenopausal females only; if required)	Х																			
Electrocardiogram h	Х		Х						Χ		Х					Х		Х		Х
Vital Signs ⁱ	Х		Х			Х			Χ		Х		Х	Х		Х		Х		Х
Pulse Oximetry	Х		Х			Х			Χ		Х		Х	Х		Х		Х		Х
Spirometry	Х		Х			Х			Χ		Х		Х			Х				
Adverse Events	•									ı	I	1		1	ı	I			I	—
Concomitant Medication	•																			———
Blood Samples for PK assessments			Х					Х	Х	Х	Х			Х						

Part 1 Footnotes

ADM - admission

EDV - Early Discontinuation Visit

- a. Subjects will return on Day 5 for safety evaluations.
- b. Screening procedures (including informed consent) can be performed over more than 1 day. Repeat of study procedures is permitted on the day and/or on another day (as appropriate) at the discretion of the investigator.
- c. Height and Weight at screening. Weight only on Day 1 (pre-dose).
- d. All female subjects.
- e. Discharge from clinic after completion of 24 hour post-dose assessments.
- f. Full physical examination at screening, Day 5 and EDV. Symptom directed examination; if required at any other visits or times at the discretion of the investigator.
- g. Clinical safety laboratory samples (clinical chemistry, haematology and urinalysis) must be performed within 7 days of Day 1; if this interval is exceeded, sampling must be repeated. Samples for clinical chemistry will be obtained following a fast of at least 8 hours (water permitted).
- h. Performed in triplicate. For assessment of time windows, the time of the first ECG of the triplicate will be used.
- i. Systolic and diastolic blood pressure, pulse rate and respiratory rate. Tympanic temperature measured at screening and pre-dose only.

CONFIDENTIAL

Clinical Pharmacology Study in Healthy and Asthmatic Subjects
Clinical Study Protocol – Study Z7240J01 Version Final 1.2; 04 June 2020Amendment 02

Permitted windows for all relevant procedures and dosing will be provided in the Study Reference Manual. Where the protocol requires more than one procedure to be completed at the same time point, all efforts will be made to obtain the PK samples at the exact nominal time relative to dosing. Any other procedures scheduled at the same time point will be performed either before or after the PK, as appropriate.

1.2.2. Schedule of Activities for Part 2 (MAD – Mild Asthmatics)

Study Day	-28 to -1	-4/- 3 ^{bb}	-1					Tre	atme	ent P	erio	t					Return Visits ^a		Follow-up Phone Call	EDV
					1		2	3	4	5	6	7	8	9	10	11	14	17	11 to 17 days after last dose	
Study Procedures ^b	Screening		Adm	Pre- dose	0	Post- dose														
Residential Period			•						→						•	→				
Informed Consent	X																			
Medical History (including demographics)	Х																			
Weight and Height c	Х			Х																
Vein Assessment	Х																			
Urine Drug Screen (including Cotinine)	Х		Х																	
Alcohol Breath Test	Х		Х																	
Serum Pregnancy Test d	Х																			
Urine Pregnancy Test d				Х														Х		Х
Inhaler Device Training	Xcc			Х																
Discharge from the Clinic e									Χ							Χ				
Physical Examination f	X		Х	Х		Х	Χ	Χ	Χ	Χ	Χ	Х	Χ	Χ	Χ	Х	X	X		Χ
Safety Labs ^g	X						Xh					Xi				X ^j		X		Χ
Serology (HIV/Hepatitis screen)	X																			
FSH (postmenopausal females only; if required)	X																			
SARS-CoV-2 Testaa		Х																		
Electrocardiogram k	Х			Х		ΧI	Xh			Xi					Xm			Х		Х
Vital Signs ⁿ	Х			Х		Χ٥	Xh	Xi	Xi	Xi	Xi	Xi	Xi	Xi	Хp	Χj	Х	Х		Х
Tympanic Body Temperature	Х	Х	Х	Х			Χ	Χ	Χ	Х	Χ	Х	Х	Χ	Х	Х	Х	Х		Х
Pulse Oximetry	Х			Х		Χ°	Xh	Xi	Xi	Xi	Xi	Xi	Xi	Xi	Хp	X j		Х		Х
Spirometry q	X			X		Xr	Xh	Xi	Xi	Xi	Xi	Xi	Xi	Xi	Xs	Χj	Х	Х		X
Adverse Events	→																			
Concomitant Medications	-																			→

Study Day	-28 to -1	-4/- 3 ^{bb}	-1					Tre	atme	ent P	erio	t					Ret Visi	-	Follow-up Phone Call	EDV
					1		2	3	4	5	6	7	8	9	10	11	14	17	11 to 17 days after last dose	
Study Procedures ^b	Screening		Adm	Pre-		Post-														
IMP Administration ^t				dose	Х	dose	Х	Х			Х		Х	Х	Х					
Blood Samples for PK assessments				Х	^	Xu	Λ	Xi	Xi	Xi	Xi	Xi	Xi	Xi	Χw	Χj	Χ			Ху
Induced Sputum Samples for PK assessments											X	, ,							Xz	

ADM - admission

Part 2 Footnotes

EDV – Early Discontinuation Visit

- a. Subjects will return on Day 14 and Day 17 for PK sample collection (Day 14 only) and safety evaluations.
- b. Screening procedures (including informed consent) can be performed over more than 1 day. Repeat of study procedures is permitted on the day and/or on another day (as appropriate) at the discretion of the investigator. In the event of BID dosing; assessments will be performed relative to the 0-hour dose only.
- c. Height and Weight at screening. Weight only on Day 1 (pre 0-hour dose).
- d. All female subjects.
- e. Residential Periods: Discharge from clinic after completion of Day 4 and Day 11 assessments as applicable.
- f. Full physical examination at screening, Day 17 and EDV. Symptom directed examination; if required at any other visits or times at the discretion of the investigator.
- g. Clinical safety laboratory samples (clinical chemistry, haematology and urinalysis) must be performed within 7 days of Day 1; if this interval is exceeded, sampling must be repeated. Samples for clinical chemistry will be obtained following a fast of at least 8 hours (water permitted).
- h. 24 hours post 0-hour dose Day 1 and prior to Day 2, 0-hour dose administration.
- i. Prior to 0-hour dosing.
- j. 24 hours post the 0-hour dose on Day 10.
- k. Performed in triplicate. For assessment of time windows, the time of the first ECG of the triplicate will be used.
- I. Performed at 2 and 4 hours post 0-hour dose.
- m. Pre-dose (0-hour) and post 0-hour dose at 2 and 4 hours.
- n. Systolic and diastolic blood pressure, pulse rate and respiratory rate.
- o. Performed at 0.5, 2, 4, 8 and 12 hours post 0-hour dose. If dosing is BID, the 12-hour assessment will be performed before the evening (i.e. 12-hour) dose.

- p. Pre-dose (0-hour) and post 0-hour dose at 0.5, 2, 4, 8 and 12 hours.
- q. Pre- and post-bronchodilator (salbutamol) reversibility testing at screening. At all other visits and time-points, spirometry may be performed pre- or post-bronchodilator; i.e. there are no requirements for bronchodilator restrictions after the screening visit.
- r. Performed at 0.5, 2, 4 and 8 hours post 0-hour dose.
- s. Pre-dose (0-hour) and post 0-hour dose at 0.5, 2, 4 and 8 hours.
- t. On Days 4 to 9 the subjects will be required to attend the unit for the evening for their 12-hour dose (i.e. return in the evening on Day 4 and attend twice daily on Days 5 to 9) if dosing is BID.
- u. **PK blood samples**: at 1.5, 2, 3, 4 and 12 hours post 0-hour dose. If dosing is BID, the 12-hour sample will be collected before the evening (i.e. 12-hour) dose.
- v. **PK blood sample:** at 24 hours post 0-hour dose Day 1 and prior to Day 2, 0-hour dose administration. If dosing is BID, the 24 hour sample can be taken anytime pre-dose on Day 2.
- w. PK blood samples: Pre-dose (0 hour) and post 0-hour dose at 1.5, 2, 3, 4 and 12 hours.
- x. Induced Sputum Samples for PK assessments: Pre-dose (0 hour) and post 0-hour dose at 3 hours and 6 hours.
- y. PK blood sample: Only required if EDV is performed up to and including Day 14.
- z. Induced Sputum Samples for PK assessments: Only required if EDV is performed up to and including Day 7.
- aa. Subjects will undergo a SARS-COV-2 RT-PCR test. Subjects testing negative may proceed to enrol in the study, provided other eligibility criteria are met; Subjects who test positive should be withdrawn from screening for the study and undergo or be referred for appropriate medical care as determined by local policy for managing a positive result. SARS-COV-2 RT-PCR test may be conducted at any time between Day -4 and Day -3 at the discretion of the site. Additional RT-PCR testing may be performed throughout the study if deemed necessary by the investigator.
- bb. Day -4/-3 procedures may be performed on the same day as the screening procedures if screening is performed within 3 or 4 days of dosing.
- cc. Inhaler device training at screening is to be a demonstration only.

Permitted windows for all relevant procedures and dosing will be provided in the Study Reference Manual. Where the protocol requires more than one procedure to be completed at the same time point, all efforts will be made to obtain the PK samples at the exact nominal time relative to dosing. Any other procedures scheduled at the same time point will be performed either before or after the PK, as appropriate.

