6.6.2. Part 2 (MAD)

Dose administration in Part 2 may only commence after completion of SAD cohort 2 in Part 1 and review of safety data up to a minimum of 24 hours post-dose.

The decision to proceed with Part 2 and dose escalation decisions between MAD cohorts will be made at an interim data review after dose administration in each cohort.

Progression to the next dose group will be permitted after review of safety data suggests that it is safe to do so.

The starting dose for Part 2 MAD will be confirmed during an interim review of safety data from the completed SAD cohorts. The dose to be administered in MAD cohort 2 will be based on emerging data and will not exceed the highest dose investigated in the SAD cohorts.

For dose escalation to proceed in MAD cohort 2, data must be available from a minimum of 4 dosed subjects from MAD cohort 1 (defined in Section 4.1.2) who have completed the planned safety assessments up to a minimum of 24 hours after dosing on Day 10 and up to a minimum of 24 hours post-dose from SAD cohort 3. For dose escalation to proceed in MAD cohort 3, data must be available from a minimum of 4 dosed subjects from MAD cohort 2 (defined in Section 4.1.2) who have completed the planned safety assessments up to a minimum of 24 hours after dosing on Day 10 and up to a minimum of 24 hours post-dose from SAD cohort 4.

The decision to proceed will only be made if all parties agree and if it is clear from the safety data that it is appropriate to proceed with the next cohort. If data in fewer than 6 subjects are considered acceptable to proceed, additional subjects will not be dosed to increase the number of subjects in the completed cohort for dose escalation purposes.

6.6.3. Part 1 (SAD) to Part 3

The oral dose of voriconazole to be administered in Part 3 is 200 mg.

The inhaled ZP-059 dose to be administered in Part 3 will be confirmed after completion of SAD cohorts 1 to 4. Hence, dosing of Part 3 may occur prior to/in parallel with dosing in Part 2.

The dose decision will be made at an interim review of available safety data from Part 1 SAD cohorts (see Section 6.6.1). For dose administration to proceed, data must be available from a minimum of 4 dosed subjects in each of SAD cohorts 1, 2, 3 and 4 who have completed the planned safety assessments up to a minimum of 24 hours after dosing. The decision to proceed will only be made if all parties agree and if it is clear from the safety data that it is appropriate to proceed.

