6.6.4. Criteria for Safety Advisory Committee

Dose levels for each cohort (Parts 1 and 2) and Part 3 will be decided during the SAC meetings.

The SAC may also agree for additional subjects to be included for an intermediate dose level if warranted or may agree to reduce or increase (see Section 4.3) the dose. Any decision to investigate an intermediate or reduced dose level will be fully documented.

The decision to proceed to the next higher dose level will be based on safety and tolerability data. The following data (minimum of 24 hours post-dose) are required for dose escalation decisions:

- Adverse events
- Vital signs (including systolic and diastolic blood pressure, pulse rate, respiratory rate and pulse oximetry)
- Safety laboratory (including clinical chemistry, haematology and urinalysis)
- ECG
- Physical examinations
- Spirometry assessments (including FEV₁, forced vital capacity [FVC], peak expiratory flow rate [PEFR] and FEV₁/FVC)

If, following review by the SAC it is deemed acceptable to continue dose escalation above the maximum dose described in this protocol (40 mg ZP-059), a substantial amendment with relevant data will be submitted for approval to the regulatory authorities and ethics committee (EC).

Dose escalation will not occur if:

 One or more subjects in a cohort experiences a serious adverse event (SAE) related to IMP.

٥r

 Two or more subjects in a cohort experiences severe non-serious AEs related to IMP.

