8.12.6. Cardiovascular and Death Events

Voriconazole has been associated with QTc interval prolongation. There have been rare cases of torsade de pointes in patients taking voriconazole, who also had risk factors such as cardiomyopathy.

Voriconazole should be administered with caution to patients with predisposing cardiac related problems and also with concomitant therapy which is known to prolong QTc interval. Additionally, any patients taking medications that are known to prolong QTc interval will be excluded from the study.

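### The escalation rule calls for ECG data to at least 24 hours after the Day 10 dose, but the Part 2 schedule has no ECG between 4 hours on Day 10 and Day 17

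*Protocol*

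**What the plan says.** Protocol section 6.6.4 introduces the SAC's data list with "The following data (minimum of 24 hours post-dose) are required for dose escalation decisions". Six types follow: adverse events, vital signs with pulse oximetry, safety laboratory tests, ECG, physical examination and spirometry.

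Section 6.6.2 says where the 24 hours start in Part 2. For the steps to MAD cohort 2 and MAD cohort 3, at least 4 dosed subjects of the preceding MAD cohort must have "completed the planned safety assessments up to a minimum of 24 hours after dosing on Day 10". Single-dose data to 24 hours from SAD cohort 3 or 4 are needed as well.

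The Part 2 schedule of activities (section 1.2.2) marks ECGs at screening, on Day 1 (pre-dose, 2 h and 4 h), on Day 2, on Day 5 before dosing, on Day 10, on Day 17 and at early discontinuation. Footnote m gives the Day 10 times: "Pre-dose (0-hour) and post 0-hour dose at 2 and 4 hours". The Day 11 and Day 14 cells are empty. In the Day 11 column other rows carry footnote j: "24 hours post the 0-hour dose on Day 10".

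Section 8.12.6 states: "Voriconazole has been associated with QTc interval prolongation". Section 7.1 sets QTcF withdrawal limits, and section 3.2.1 includes ECG in the safety endpoint.

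**The concern.** A site that follows the schedule exactly does not produce one of the inputs that the escalation rule lists as required. The SAC could meet at the earliest point that 6.6.2 allows and find the ECG record ending at 4 hours, while the other measured types run to 24 hours.

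At stake is the cardiac information behind the choice of dose for MAD cohorts 2 and 3, for a drug with a stated QTc signal. There is also a smaller reporting effect. SAP section 7.13.5 summarises ECG values and changes from baseline over time, and that summary would hold a 24-hour value after the first dose but none after the last.

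**Working it through.** The point involves no power or sample-size figure. The check sets the data list in 6.6.4 against the Day 11 column of 1.2.2, then works out the time gaps.

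**Required data against scheduled data, 24 h after the Day 10 dose**

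| Data type in 6.6.4 | Day 11 entry in 1.2.2 |
|---|---|
| Adverse events | collected continuously |
| Vital signs | yes, footnote j |
| Pulse oximetry (listed with vital signs) | yes, footnote j |
| Safety labs | yes, footnote j |
| Spirometry | yes, footnote j |
| Physical examination | marked, but footnote f makes it symptom-directed and only if required |
| ECG | none |

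**Time gaps on scheduled ECGs**

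- Shortfall at the minimum cut: 24 h − 4 h = 20 h.
- Day 10 dose to the next ECG on Day 17: (17 − 10) × 24 = 168 h nominal.
- From the 4 h ECG to Day 17: 168 − 4 = 164 h.

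These hold for both regimens, because the last dose is on the morning of Day 10 whether dosing is once or twice daily (section 4.1.2).

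**ECGs at the end of an earlier dosing interval**

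- After the first dose: the Day 2 ECG, "24 hours post 0-hour dose Day 1 and prior to Day 2, 0-hour dose administration" (footnote h). This is 24 h after dose 1 under once-daily dosing. Under twice-daily dosing it is 24 h after the first dose but about 12 h after the evening dose.
- Once daily, Day 5 pre-dose: about 24 h after the Day 4 dose.
- Once daily, Day 10 pre-dose: about 24 h after the Day 9 dose, that is after nine doses.
- Twice daily, Days 5 and 10 pre-dose: from Hour 12 of the previous day to Hour 0, about 12 h.

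**Who is affected**

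- The two planned MAD escalations rest on MAD cohorts 1 and 2: 2 × 6 = 12 planned subjects, with a minimum of 2 × 4 = 8 providing data.
- MAD cohort 3 follows the same schedule, but no planned escalation depends on it.
- The MAD cohort 1 starting dose and the Part 3 dose rest on SAD data, and the Part 1 schedule has a 24-hour ECG.

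**Is the blank cell real?** Each of the six Part 2 rows checked (ECG, vital signs, labs, oximetry, spirometry, physical examination) has a label and 20 columns, and the ECG marks line up with the day headings. Footnote m independently confirms that the Day 10 readings end at 4 h. A caution remains: the dosing row of the same table lacks marks on Days 4, 5 and 7 although dosing is daily, so some marks in this table were lost in text extraction. That row sits in a visibly more damaged block than the ECG row.

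**The case against.** The strongest reply is that 6.6.2 is the rule specific to Part 2 and asks only for completion of the *planned* assessments. A subject who has had every ECG in the schedule meets that condition. Section 6.6.4 is a general list for all parts, and its 24 hours can be read as a follow-up window and not as a measurement time for each item. The physical examination supports this reading: it is on the list, yet is not guaranteed on Day 11 either. This softens the conflict. It does not remove it, because 6.6.4 attaches the 24 hours to a list that names ECG, and no text says that a 4-hour ECG is enough.

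It can also be said that the SAC may have more than the minimum. It may meet later and see Day 17, it may review additional data (section 6.6), and extra ECGs are allowed (section 8.11.11). It also has single-dose 24-hour ECGs from SAD cohorts 3 and 4. All of that is correct, but none of it requires an ECG 24 hours after the last of the repeated doses. Unscheduled post-baseline ECGs would also be listed and not tabulated (SAP section 7.5.3).

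A reader might infer two stronger things that the documents do not support:

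- *That every MAD escalation will be decided on ECGs stopping at 4 hours.* The 24 hours is a minimum, so this describes only scheduled ECGs at the earliest permitted decision.
- *That Part 2 has no 24-hour ECG at all after repeated dosing.* Under once-daily dosing, the pre-dose readings on Days 5 and 10 are such ECGs. What is missing is the reading 24 hours after the final dose.

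**Conclusion.** The mismatch between 6.6.4, read with 6.6.2, and the ECG row of 1.2.2 is real and should be settled before the first MAD escalation. ECG is the only measured type on the SAC's list with no Day 11 entry of any kind. At the minimum data cut, the two planned MAD escalations would rest on scheduled ECGs that end 20 hours short of the stated window.

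The gap is wider in practice under twice-daily dosing, where no scheduled ECG after the first day's dosing and before Day 17 is further than about 12 hours from the previous dose. Under once-daily dosing the Day 10 pre-dose ECG, about 24 hours after the ninth dose, partly fills it.

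The conclusion rests on three assumptions: that the blank Day 11 ECG cell is in the source table, that the SAC meets at the earliest time 6.6.2 permits, and that no unscheduled ECG is taken.

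**What to change.** Reconcile sections 6.6.4 and 6.6.2 with the ECG row and footnotes of section 1.2.2, so that the ECG data the SAC must have and the ECGs the schedule collects are the same. Either the list or the schedule can change; which is for the sponsor to decide. The text should state, for each listed data type, whether the 24 hours is a required assessment time or only the length of follow-up. That would also settle the status of the symptom-directed physical examination on Day 11.

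If a Day 11 ECG time point results, it should enter the by-time summary in SAP section 7.13.5 as a scheduled assessment.

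The cost is a clarifying sentence or a one-cell change to the table, made by amendment before the first MAD escalation. Subjects are already resident until 24 hours after the last dose under the present schedule, so neither route adds a visit.
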